## Introduction

While first-line pharmacotherapies for nicotine dependence (i.e. varenicline) demonstrate efficacy for short term smoking cessation, relapse remains a challenge in smokers. Growing evidence implicates the insula in cigarette craving and cue-induced relapse, with studies showing improved abstinence rates following deep repetitive transcranial magnetic stimulation to this region. The present proposal aims to optimize smoking cessation outcomes in a generalizable group of smokers by combining currently approved pharmacotherapy (varenicline) with deep repetitive transcranial magnetic stimulation (rTMS), a novel therapeutic intervention with recently evidenced efficacy for smoking abstinence. Such a combined approach may improve abstinence rates in smokers through the synergistic action of these two separate interventions, targeting both cessation and relapse.

## Background and Rationale

Although currently available pharmacotherapies for nicotine dependence have evidenced considerable efficacy in short term smoking outcomes, randomized trials reveal nearly three quarters of initial quitters relapse within a year [1, 2]. The risk for smoking relapse [3] and unsuccessful quit rates following pharmacotherapy treatment [4] are even higher among certain subgroups of smokers who are largely excluded from clinical trials (i.e., those with psychiatric and/or substance use co-morbidity) [5]. While varenicline demonstrates superiority over other first-line medications for smoking cessation [6], the probability of smoking relapse signals a clear need for improvement [7]. Indeed, novel multifaceted treatment approaches which in combination successfully address both cessation and relapse prevention are required to treat this complex disorder.

Varenicline: a novel therapeutic approach for smokers: The nicotinic acetylcholine receptors (nAChRs) are ligand-gated ion channels composed of five subunits, labeled  $\alpha_2$  to  $\alpha_{10}$  and  $\beta_2$  to  $\beta_4$  in the central nervous system. The combination of subunits determines the functionality of the receptor. In the brain, the most prevalent of these are the homo-oligomeric  $\alpha_7$  and the heteromeric  $\alpha_4\beta_2$  nAChRs. A large body of evidence implicates  $\alpha_4\beta_2$  nAChRs in the reinforcing effects of nicotine [8-10]. Notably, the  $\alpha_4\beta_2$  nicotinic acetylcholine receptors located in the midbrain area are critical for nicotine's ability to increase DA levels in the nucleus accumbens [11-15], an important factor linked to the motivational and reinforcing properties of drugs of abuse [16]. Recently, a partial agonist of the  $\alpha_4\beta_2$  nAChRs (varenicline), approved as a smoking cessation aid, has become available [17,18]. Varenicline has high affinity for  $\alpha_4\beta_2$  ( $K_i$   $\alpha_4\beta_2$  = 0.4 nM) and much less for other human nAChRs ( $K_i$   $\alpha_7$  = 125 nM;  $K_i$   $\alpha_3\beta_4$  = 86 nM;  $K_i$   $\alpha_6/\alpha_3\beta_4$  = 111 nM) [19]. The rationale to develop partial agonist for smoking cessation was to have a duality of effect: acting as an antagonist to block the rewarding/reinforcing effect of nicotine while smoking; acting as an agonist to attenuate withdrawal and cravings due to abstinence [20]. By correlating free human brain concentrations, estimated from therapeutic human plasma levels and rat brain-to-plasma ratios, with binding affinities and functional potencies at  $\alpha_4\beta_2$  nAChRs, Rollema *et al.* found that concentrations equal to predicted human brain concentration of varenicline can extensively desensitize and to a lesser extent activate  $\alpha_4\beta_2$  in vitro [19], but minimal effect at  $\alpha_7$  nAChRs is expected [19]. Therefore, it is likely that the effects of varenicline in humans are mediated by  $\alpha_4\beta_2$  nAChRs [19].

Repeated Transcranial Magnetic Stimulation (rTMS) as an innovative approach: rTMS is a technique that has been found to be useful as a potential treatment for neuropsychiatric diseases. rTMS is almost painless, does not require anesthesia, and is not associated with significant side effects. There is compelling evidence that rTMS works by affecting the function of neuronal circuits and inducing local changes in neural excitability. Transient inactivation of a specific brain structure can also be induced in humans through rTMS, through mechanisms that are likely associated with potentiation of GABAB receptor mediated inhibitory neurotransmission [21]. However, rTMS effects are complex and likely involve local modifications in the dynamic release patterns of various neurotransmitters, including dopamine [22-26]. The fact that there is *in vivo* evidence that rTMS of frontal brain regions has a modulatory effect on dopaminergic system, suggest that rTMS may be particularly useful in neuropsychiatric disorders associated with dopamine dysfunction, such as addiction [25, 27]. Moreover, with the recent development of Deep rTMS H-coils by [name] (a consultant on this protocol), it has become feasible to perform rTMS on deeper brain structures such as the insula [28-30].

Insula as a target structure: Several lines of research implicate the insula as a critical substrate in nicotine dependence following evidence that insular lesions produce a loss of self-reported cravings for cigarettes and immediate cessation of smoking without relapse [31,32]. As proposed by Naqvi *et al.*, the insula plays a role in the recall of the interoceptive effects of drug taking, and through interactions with other brain regions, mediates conscious urges and decision making precipitating relapse [33]. This hypothesis is substantiated by growing preclinical work: results from studies at our own translational addiction research laboratory reveal that temporary insular inactivation in rats leads to reduced nicotine self-administration and seeking after exposure to nicotine-associated cues or a priming dose [34,35]. Neuroimaging studies further evidence significant associations between cue-induced activation of the insula and self-reported craving for a cigarette [36], with greater bilateral insular pre-quit activity also predicting relapse in smokers [37].

Taken collectively, an intervention which directly modulates insular electrical activity such as deep rTMS may be promising treatment for nicotine dependence. Indeed, a recent investigation revealed improved smoking outcomes following high-frequency deep rTMS non-selectively targeting the insula and prefrontal cortex relative to sham. Specifically, smokers reported reduced cigarette consumption and greater and longer lasting abstinence rates after 2 weeks of treatment [38]. However, the effect of stimulation exclusively to the insula remains to be thoroughly explored in humans. The use of the recently developed H-coil will allow us to address this gap. Although the modulation of structures adjacent to the insula cannot be excluded, this will unlikely be a drawback as results in human smokers suggest that extra-insular lesions do not implicate those areas in smoking behaviors [31]. Similarly, pilot studies from our lab evaluating the effect of inactivating brain areas adjacent to the insula found no significant effects ([name] *et al.*, unpublished observations). We recently also completed a rTMS study with the H-coil in healthy non-dependent individuals, and our data indicate that our approach is safe and tolerable in humans (data not shown). Finally, as some of varenicline's actions involve down-regulation of the functional connectivity between the insula and regions pertinent to nicotine withdrawal in smokers [39], the combination of varenicline and deep rTMS of the insula is a favorable dual treatment approach. These interventions may synergistically work to yield more efficacious and enduring treatment effects.

## Research Question

Can deep rTMS to the insula using the insula H-coil improve smoking outcomes in smokers receiving varenicline?

## Aims and Hypotheses

### *Hypotheses:*

Primary: Active deep rTMS intervention will improve point prevalence abstinence rates at the end of varenicline treatment (Week 12) as measured by self-report and confirmed with plasma cotinine levels.

Secondary 1: Active deep rTMS intervention will significantly attenuate craving and reduce cigarette consumption and dependence severity.

Secondary 2: Active deep rTMS intervention will significantly improve short-term point prevalence abstinence rates and long-term prolonged and continuous abstinence rates.

### *Aims:*

Primary: To examine the efficacy of bilateral deep repeated transcranial magnetic stimulation (rTMS; 10 Hz) directed to the insular cortex, relative to sham stimulation, on point prevalence smoking abstinence in smokers who are receiving standard varenicline treatment (2 mg/day).

Secondary 1: To examine the effect of bilateral deep rTMS directed to the insular cortex, relative to sham, on other smoking outcomes throughout study duration including self-reported craving, cigarette smoking and dependence severity.

Secondary 2: To examine the effect of bilateral deep rTMS directed to the insular cortex, relative to sham, on abstinence at the end of rTMS treatment (point-prevalence abstinence at Week 4) and at 6-month follow-up (prolonged and continuous abstinence at Week 26).

## Study Design

Overview: This study will be a randomized, double-blind, sham-controlled clinical trial. Specifically, fifty nicotine dependent participants expressing a willingness to quit smoking will be randomized into one of two rTMS intervention arms: Sham (n=25) or Active (10 Hz, n=25). All participants will receive an open-label treatment of varenicline (Week 1 to Week 12), and a target quit date (corresponding to the end of Week 2) will be set for each individual. Participants will also receive brief weekly counselling adapted from the Mayo Clinic's 'Smoke Free and Living It' manual. The rTMS interventions will begin at Week 1 for four weeks (5 sessions a week for a total of 20 sessions), and will be performed with an insula-targeting H-coil. Moreover, follow-up visits will be scheduled weekly for the duration of the medication phase and on Week 26. The primary outcome of the proposed study will be plasma cotinine verified (<15 ng/ml) 7-day point prevalence abstinence as measured at the end of Week 12. Other smoking outcomes (craving, consumption patterns, and dependence) will be captured through standardized questionnaires throughout the study duration. Participants will also have plasma cotinine verified measurements of abstinence at the end of rTMS treatment (end of Week 4), and at the follow-up at 6 months (end of Week 26). This trial will be conducted in compliance with the protocol, GCP, and Canadian Food and Drug Regulations Division 5.

Participants: Participants in the proposed study will be nicotine dependent individuals (n=50). We will recruit through various sources: the community, CAMH clinics, word of mouth, and/or through posters/fliers distributed in and around the research centers as well as on the CAMH website. CAMH approved study recruitment ads will be placed primarily around, but not limited to, the downtown Toronto area. Ads may also be placed in various local newspapers, magazines, community venues (e.g., bars) as well as TTC streetcars, buses and subways. Online advertisement services may be employed, in accordance with CAMH guidelines. Ads and fliers will be approved by the REB. Participants may also be recruited from similar protocols approved at CAMH provided they have agreed to being contacted about future studies.

Recruitment for the study may also be initiated by members of the *Circle of Care* who are treating the potential study participant. These individuals will not obtain consent but they may identify potential research participants and obtain verbal permission for a member of the research team to approach and discuss the study with them. Potential participants who provide assent to be contacted by a member of the research team will then be contacted by a member of the research team who will engage them in the informed consent process if they are agreeable to proceed as such.

Additionally, as part of the CLEARR (Clinical Engagement and Research Recruitment) initiative, a delegated Research Coordinator under the supervision of a CLEARR team recruiting clinician and accountable to the Manager of Research Practice will identify potential participants and notify the research team and the client's clinician about the potential eligibility to participate in the study. The clinician will then ask the client for assent to meet with a study team member to discuss details and participation in the study. Only clients who agree to this process will be approached.

The delegated research Coordinator will access personal health information (PHI) in I-CARE in order to determine eligibility of CAMH participants to participate in the research study. No PHI except MRN will be collected for this purpose and this information will be kept in a secure locked location.

The aforementioned recruitment strategies are in line with our aim to enroll a representative sample of smokers. This is in contrast to more traditional smoking cessation clinical trials, wherein the majority of smokers are often excluded, thereby jeopardizing the generalizability of the data [5]. Our exclusion criteria may be regarded as less restrictive for this purpose. Nicotine dependence will be determined via testing/ measurements stated in the "Screening Assessment" section below.

Interventions and Procedures: Potential participants will undergo a telephone pre-screen to determine initial eligibility. Participants may also complete this screening electronically, through REDCap (see REDCap section). They will subsequently be invited to an in-person Screening Assessment to confirm final eligibility to participate.

#### *Screening Assessment and Consent:*

Following the review and signing of the Informed Consent Form, the following measures and assessments will be administered at the screening visit:

- 1) Fagerstrom Test of Nicotine Dependence (FTND). The FTND is a measure of physical dependence severity [40].
- 2) Diagnostic and Statistical Manual of Mental Disorders (DSM-V/SCID-V). The DSM/SCID-V will be used to diagnose nicotine dependence in participants [41] and/or any other psychiatric issues.
- 3) Timeline Follow-Back (TLFB). The TLFB is a reliable method used to detail nicotine (smoking), alcohol and caffeine consumption behavior over a specified period of time. Participants are asked to recall key anchoring events to prompt retrospective estimates of cigarette, alcohol or caffeine intake [42].
- 4) Expired Carbon Monoxide (CO) Measurements. Breath CO measurements provide a reliable indication of recent smoking status among smokers.
- 5) Smoking Contemplation Ladder. This questionnaire allows for the measure of readiness to quit smoking in individuals. A cutoff score of 7 is commonly used to determine individuals who are motivated to quit [43].
- 6) Mini Mental State Examination (MMSE). The MMSE is a gross measure of cognitive status in individuals, with a commonly used cutoff of <24 [44]. The test will serve as indication of cognitive competence to provide informed consent.
- 7) Medical and/or psychiatric assessment by study physician (or delegate).
- 8) Blood draw for quantification of cotinine, complete blood cell count, routine blood chemistry and/or beta-HCG (serum pregnancy test, for females).
- 9) SAFTEE: a technique for the systematic assessment of side effects in clinical trials [45].
- 10) Drug screen (urine or blood)
- 11) Demographic and contact forms
- 12) TASS form (TMS Adult Safety Screening Questionnaire)

*Total Number of Study Visits:*

In addition to the screening assessment, there will be 30 study visits. The first visit (study start day) will correspond to the 1st varenicline dose and the 1st rTMS session. There will be 4 consecutive weeks of rTMS (20 sessions). Weekly follow-up visits will occur for the 12 weeks of the trial and a final visit will occur at week 26. The TLFB, SAFTEE, concomitant medication log and Adverse Event log will be administered/ updated at every visit. CO measurements will also be taken at every visit. Regular pregnancy testing for females will occur throughout the study. Selective questionnaires (described below in Outcome Measures) will also be administered at study sessions. Urine drug testing will be conducted as required. There will be a total of 4 blood draws (including the screening session). Cotinine blood samples will not be analyzed upon collection. The clinical lab will process the samples and the study staff will pick up the samples and store them in a -20°C freezer. Analysis will be done in batches of 30 or more samples.

*Varenicline Treatment:*

All participants will receive varenicline pharmacotherapy, beginning at Week 1, for a total duration of 3 months (12 weeks). A target quit date for all participants will be set for Day 15. The varenicline dosage schedule will be that standard for smoking cessation. It will consist of 0.5 mg tablet once a day for the first three days (day 1 – day 3), followed by four days of 0.5 mg BID (i.e. twice a day: AM and PM; day 4-7). The target daily dose of 2 mg (1 mg BID, i.e. twice

a day: AM and PM) will begin on Week 2 (day 8) and extend until the end of treatment. Subjects will be advised to orally consume the tablet with food and water. Notably, we may use 1 mg daily if 2 mg daily is not well tolerated. The study medication will be dispensed weekly by the CAMH pharmacy. Compliance will be assessed through reported missed doses at weekly visits (see *Follow-up Visits* section below).

*rTMS:*

Participants will be randomized into either sham (n=25) or active (10Hz, n=25) rTMS intervention in a 1:1 ratio. Brainsway will provide the randomization cards and the randomization list, which will then be managed by an independent person outside of the study. The stimulation protocol will begin in Week 1, and will consist of 5 rTMS sessions per week over the course of 4 weeks (20 in total). Importantly, rTMS will be administered 2 weeks preceding and 2 weeks following the targeted quit date (Day 15), as smokers are believed to be most susceptible to relapse early in the abstinence phase [46]. Both active and sham stimulations will be administered using the insula H-Coil (Brainsway, Model 102B; Jerusalem, Israel), developed by [name] (consultant on this proposal). First, resting motor threshold (RMT) will be determined based on the minimum intensity to cause one of the right hand muscles to activate in at least 5 of 10 trials. The active simulation will comprise of 34 trains of 3 seconds each at 10 Hz and 30 pulses per train and an inter-train interval of 26 seconds. Stimulation intensity will be administered at a target of 120% RMT. Titration of stimulus intensity may occur over the first 4 sessions to enhance tolerability. For participants with poor tolerability the stimulation target will be a minimum of 110% RMT. For the sham stimulation, we will use the same coil placement as that used for active stimulation, matching the number of pulses delivered. The sham coil, which is built into the same helmet, mimics the active coil with respect to acoustics and scalp sensation. Notably, this coil, which allows for the bilateral stimulation of the insular cortex, is presently located at CAMH, and has been used by our team in a recently completed pilot study in healthy controls. Since rTMS sessions will occur daily for 4 weeks, medical staff will be onsite during all procedures and standard procedures for treating patients with rTMS in the Temerty Centre will followed.

*Follow-up Visits:*

The follow-up visits scheduled on a weekly basis for the duration of the medication phase (Week 1 through to Week 12) will serve a number of purposes. First, as counselling is clinically recommended to be administered alongside smoking cessation medication for increased efficacy [47], a trained study member will deliver brief counselling interventions. The counselling sessions will be adapted from the Mayo Clinic ‘Smoke Free and Living It’, a commonly used manual in pharmacotherapy trials for nicotine dependence, and will cover various topics aimed at building problem-solving skills and providing support through quitting and withdrawal [48]. Counselling will be provided weekly for the 12 weeks. Second, adverse events will be recorded, and medication compliance will be monitored at follow-up visits. Third, questionnaires will be administered to assess the secondary outcome measures and suicidality of this study (details below).

Clinical study staff may access I-CARE for research record updating as this is a treatment study.

*Summary of Events:*

Below is a table outlining the assessments, measures, and treatments done at each visit.

	Week and Visit Number															
			W1		W2		W3		W4		W5	W6-8	W9	W10-12	W13	W26
	1*	2	3 to 6	7	8 to 11	12	13 to 16	17	18 to 21	22	23 to 25	26	27 to 29	30	31	
Assessments & Measures	ICF and ICF quiz	X														
	Contact & Demographic Form	X														
	Medical assessment, SCID, and ECG	X														
	TASS	X														
	MMSE	X														
	Smoking Contemplation Ladder	X														
	Blood draw	X									X			X	X	
	CO Measurement	X	X	X	X	X	X	X	X	X	X	X	X	X		
	TLFB (Cigarettes, alcohol, caffeine)	X	X	X	X	X	X	X	X	X	X	X	X	X		
	Concomitant Medication Log	X	X	X	X	X	X	X	X	X	X	X	X	X		
	AE Log	X	X	X	X	X	X	X	X	X	X	X	X	X		
	SAFTEE	X	X	X	X	X	X	X	X	X	X	X	X	X		
	Urine Drug Test	X	X		X		X		X		X	X	X	X		
	Pregnancy Test (if required)	X	X		X		X		X		X	X	X	X		
	FTND	X	X		X		X		X		X		X	X		
	Counselling		X		X		X		X		X	X	X	X		
	C-SSRS		X		X		X		X		X	X	X	X		
	T-QSU		X		X		X		X		X		X	X		
	MNSW		X		X		X		X		X		X	X		
	Point Prevalence Abstinence										X			X		
	Prolonged Abstinence													X		
	Continuous Abstinence													X		
	RMT for TMS		X													
Treatment	TMS		X	X	X	X	X	X	X	X						
	Varenicline		X	X	X	X	X	X	X	X	X	X	X			

\*Visit 1 is the screening/baseline visit.

During the TMS treatment (i.e., sessions 2-21) urine drug testing, pregnancy testing, counselling,

FTND, Columbia Suicide Severity Rating Scale (C-SSRS), T-QSU, and MNSW will be done once a week. In the event that a participant misses a session during this time where these assessments were intended to occur, they will be conducted at the following visit. Participants are intended to receive 20 TMS sessions, however, any missed TMS sessions (whether due to the participant or to holiday closure of the Temerty centre) will not be rescheduled.

During the follow up visits (i.e., sessions 22-31), in the event a subject misses a session; they will be able to reschedule the session within the same week. If they are not able to attend within the same scheduled week, the session will be considered as a missed session. The following visits will proceed as scheduled.

*COVID-19:*

All participants will be screened for COVID-19 symptoms and COVID-19 contacts. If a participant screens positive, they will not continue treatment at that time and the case will be reviewed with Infection Prevention and Control Canada (IPAC) around if, and when, treatment can resume. IPAC recommendations include that all patients and staff wear surgical masks while at CAMH (including waiting areas).

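### The same-week rule for follow-up visits does not exempt the Week 4, 12 and 26 abstinence assessments, so obtainable outcomes can go uncollected, most avoidably at Week 26

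*Combined protocol and SAP*

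**What the plan says.** The rule stands in the text after the Summary of Events table in the protocol's Study Design section. It opens with "During the follow up visits (i.e., sessions 22-31), in the event a subject misses a session", permits rescheduling inside that week, and continues: "If they are not able to attend within the same scheduled week, the session will be considered as a missed session". It closes with "The following visits will proceed as scheduled".

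In the table, the three post-screening blood draws fall at visits 22, 30 and 31, in the columns for Weeks 5, 13 and 26. They supply the cotinine confirmation for abstinence at the end of Weeks 4, 12 and 26. The primary outcome is "7-day point prevalence abstinence as measured at the end of Week 12". Three secondary outcomes (prolonged abstinence from Week 12, prolonged abstinence from Week 4, and continuous abstinence from the quit day) depend on the Week 26 visit.

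A carry-over provision exists, but only for the rTMS phase, sessions 2 to 21: "In the event that a participant misses a session during this time where these assessments were intended to occur, they will be conducted at the" next visit. It lists weekly questionnaires, counselling, and drug and pregnancy tests. Cotinine and abstinence are not on the list.

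The Data Analysis section handles missing abstinence by maximum likelihood under a missing-at-random assumption. It has no rule for an assessment obtained late.

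**The concern.** A routine visit can be skipped with little harm because another follows. An outcome visit cannot. Only four blood draws are planned, one of them at screening, so each later time point has a single sample. After visit 30 the next contact is Week 26, and after visit 31 there is none.

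The plan foresees interruptions. A positive COVID-19 screen pauses participation pending infection-control review. The withdrawal criterion for missed rTMS days sets aside holiday closures and COVID-19. The same-week rule for follow-up visits has no such allowance, even for the primary outcome.

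Two things are at stake. One is information, in a trial that the Sample Size section already describes as a pilot below 80% power. The other is the missing-at-random assumption. If people who have gone back to smoking tend to attend late, the rule turns lateness into missingness that depends on the unobserved outcome, and the mixed model cannot correct for that. This link is plausible but is an assumption. The documents do not state it.

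**Working it through.** **Timing.** Day 1 is the first dose and Week 2 starts on Day 8, so Week k ends on Day 7k.

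- Week 12 ends on Day 12 × 7 = 84. Visit 30 is in the Week 13 column, Days 85 to 91. The 7 days before a Day 85 visit are Days 78 to 84; before a Day 91 visit they are Days 84 to 90. The scheduled week therefore already gives about 7 days of slack, and the recall period only just touches treatment at its end.
- Visit 22 follows the same pattern: Week 4 ends on Day 28 and the visit is in Days 29 to 35.
- Week 26 ends on Day 26 × 7 = 182. Visit 31 is in the Week 26 column, Days 176 to 182, so the scheduled week has no days left after the nominal date.

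The table is partly broken in the text available, but all three visits lie within sessions 22 to 31 on any reading.

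**The plan's own sample size.** Inputs from the Sample Size section: 40% versus 70%, alpha 0.05 (sidedness not stated; two-sided reproduces the plan's figure), power 0.80. With mean proportion 0.55:

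- n = [1.960 × √(2 × 0.55 × 0.45) + 0.842 × √(0.40 × 0.60 + 0.70 × 0.30)]² / 0.30²
- = (1.379 + 0.565)² / 0.09 ≈ 42 per arm, matching the plan's 42.

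**Power with outcomes lost.** The same test gives power = Φ[(0.30√n − 1.379) / 0.671].

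| n per arm with a Week 12 outcome | Lost from 25 | Power |
|---|---|---|
| 25 | 0 | 0.572 |
| 23 | 2 (8%) | 0.536 |
| 22 | 3 (12%) | 0.517 |
| 20 | 5 (20%) | 0.478 |

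The plan states 0.66 at 25 per arm. That does not reproduce here (0.572); it fits 30 per arm (0.653). This is a separate matter, and only the drop from the baseline is used below.

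**Selective loss, extreme case.** At 40%, 10 of 25 in the sham arm are abstinent. If the 3 lost are all smokers, the observed rate is 10/22 = 45% with no true change.

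**Detection.** Two or three lost per arm is 4 to 6 of 50 (8% to 12%). Alone, that stays below the 10 subjects (20%) at which the plan compares participants with missing outcomes against completers.

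**The case against.** The other side has a good case, and much of it stands.

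- A reader might infer that late data are discarded. The text does not support that. It is a scheduling rule that labels a session as missed, and it says nothing about deleting a sample or self-report already obtained. Uncollected is the accurate word.
- A reader might also infer that the participant drops out of the analysis. The mixed model keeps that person's other time points; only the outcome at the missed visit is lost.
- Visits 22 and 30 already have slack, because their scheduled week follows the nominal time point. Someone a few days late can still be in time.
- A tight window has a rationale at Weeks 4 and 12, although the plan does not state it. The primary hypothesis concerns the end of varenicline treatment. Fourteen days beyond Week 13 would put the visit on Day 91 + 14 = 105, with recall over Days 98 to 104, wholly after treatment.
- The power loss is illustrative. The documents give no late-visit rate. The plan recruits 30 per arm to reach 50 completers and replaces withdrawn participants. Whether someone who misses one outcome visit still counts as a completer is undefined, so that margin may or may not absorb the loss.
- The plan allows for covariates correlated with missingness, which helps if they capture what drives lateness.

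None of this supplies an exemption for the outcome visits, and the treatment-linked rationale does not extend to Week 26.

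**Conclusion.** The point holds as a minor design weakness. The same-week rule covers every visit with a post-baseline cotinine-verified outcome. Nothing else in the documents relaxes it, and applying it as written leaves obtainable outcomes uncollected. The case is strongest at Week 26, where there is no slack after the nominal date, no later visit and no treatment-linked reason for a one-week limit. It is weaker at Weeks 4 and 12.

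The size is modest and conditional. If 2 or 3 of 25 per arm are lost, power falls by about 4 to 5 points, from 0.57 to 0.54 or 0.52. This assumes a simple two-sided pooled comparison at 25 per arm, and takes no account of the 30-per-arm recruitment or of the mixed model's other time points. Any bias rests on the further assumption that lateness is related to smoking status. A reader might infer that the primary analysis is invalid. The documents show no such thing: there is no contradiction or wrong test, only avoidable missing data and silence on how a late assessment is handled.

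**What to change.** In the Summary of Events text, exempt outcome collection (self-report and cotinine sample) at visits 22, 30 and 31 from the missed-session rule. In Data Analysis, state how late assessments are used:

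- **Week 26:** prespecify a wider window, for example up to 28 days (the figure is for the sponsor to set). Establish abstinence to the nominal date with the Timeline Follow-Back, already given at every visit, where possible. Record the sample date, and add a sensitivity analysis limited to in-week samples.
- **Weeks 4 and 12:** collect and date late self-reports and samples, keep in-week data as primary, and use the late data in a prespecified sensitivity analysis. The alternative is a short extension whose 7-day recall still overlaps treatment. On the day count above this leaves almost no room beyond Week 13, so the sensitivity analysis is the more practical choice.

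The cost is a few sentences, with no extra planned visits or blood draws. The downside is that a few assessments fall after the nominal week. This slightly lengthens time at risk for late attenders, and a positive late sample may reflect smoking after the nominal date. The change concerns outcome collection only and leaves treatment unaffected.
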